4.2 Inclusion Criteria

Patients will be eligible to enroll in study LA38-EXT if they meet all the following criteria:

- 1. Completed study LA38-0411
- 2. Females of childbearing potential must have a negative pregnancy test result at Visit 1. In addition, if applicable, they must:
 - Use an effective method of contraception according to local requirements, during the study and within 30 days following their last dose of study medication, OR
 - Have had a tubal ligation (supporting evidence required), OR
 - Have had a hysterectomy (supporting evidence required), OR
 - Participate in a non-heterosexual lifestyle, OR
 - Have a male sexual partner who has been sterilized (supporting evidence required)
- 3. Fertile heterosexual males and/or their partners must agree to use an effective method of contraception during the study and for 30 days following the last dose of study medication
- 4. All patients and/or their authorized legal representatives must provide signed and dated written informed consent prior to the first study intervention, and assent will be obtained from patients who are considered to be minors. Patients must be able to adhere to study restrictions, appointments, and evaluation schedules.

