4.3 Exclusion Criteria

Patients will be excluded from enrollment in study LA38-EXT if they meet **any** of the following criteria:

- 1. Plan to participate in another clinical trial at any time from the day of enrollment until 30 days post-treatment in the current study
- 2. For only those patients who were treated with deferoxamine in study LA38-0411 (Group 2): Presence of any medical condition (including clinically significant laboratory abnormalities, such as ALT ≥ 5 x ULN or creatinine ≥ 2 x ULN), psychological condition, or psychiatric condition which in the opinion of the investigator would cause participation in the study to be unwise.

- 3. Pregnant, breastfeeding, or planning to become pregnant during the study period.
- 4. Treatment failure after 1 year on deferiprone which in the investigator's judgment indicates the need for the patient to be started on a different iron chelator

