4.5.2 Replacement of Patients Who Withdraw

Not applicable. The only individuals eligible for enrollment are those who completed treatment in study LA38-0411.

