9.5 Criteria for Evaluability of Patient Data

All patients who were enrolled and treated with the study drug, including those who withdrew early, will be eligible for inclusion in the safety and efficacy analyses.

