3 STUDY DESIGN

LA38-EXT is a 2-year prospective, multi-center, single-arm, open-label extension of LA38-0411. All patients who have completed LA38-0411 have been offered the opportunity to continue in this extension study, with the final visit of LA38-0411 being Visit 1 of LA38-EXT. Patients who had been treated with deferiprone during LA38-0411 continued to receive deferiprone for up to 2 years (Group 1), while those who had been treated with deferoxamine were switched to deferiprone for treatment up to 2 years (Group 2) in LA38-EXT. The dosage of deferiprone was 25–33 mg/kg three times a day (t.i.d.).

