6.2.1 Intent-to-Treat Population

The ITT population will include all randomized patients who received at least one dose of study drug and have a baseline and at least one post-baseline efficacy assessment.

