6.3.3 Analysis of Efficacy

Changes in LIC, in cardiac MRI T2*, and in serum ferritin from baseline to Year 1 (both groups; Group 1 data are from LA38-0411), from baseline to Year 2 (both groups), and from

baseline to Year 3 (Group 1 only) will be summarized with descriptive statistics and will be tested against no change using a one-sample t-test. The changes in these 3 efficacy measures from the start of deferiprone therapy to the last visit of LA38-EXT in all patients, irrespective of whether deferiprone therapy was initiated in LA38-0411 or in LA38-EXT, will also be tested using a one-sample t-test. In addition, the percentages of responders will be tabulated for Year 1 (both groups; Group 1 data are from LA38-0411), for Year 2 (both groups), and for Year 3 (Group 1 only) of deferiprone therapy. The change from baseline to end of LA38-041 for deferoxamine and the change from baseline to end of LA38-EXT for deferiprone in Group 2 will be compared.

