17 TABLE SHELLS

The following table shells provide a framework for the display of data from this study. These tables may not be produced exactly as shown in the shells, but are intended to reflect the general layout of the data that will be included in the clinical study report.

Note that 'c' in the table shells indicates an alphanumeric character and 'x' indicates a number from 0 to 9.

If the same data points are collected at more than one visit, the results will be summarized in Table x.x for baseline, x.x-1 for visit 1, x.x-2 for visit 2 and so on.

Table 14.1.1 Patient disposition

	Treatment	
	DFP+ DFP	DFO+DFP
Enrolled	Xxx	xxx
Exposed*	xxx (xx%)	xxx (xx%)
Completed*	xxx (xx%)	xxx (xx%)
Withdrawn*	xxx (xx%)	xxx (xx%)

Data source: 16.2.18 Listing of disposition

Note: *Percentages are based on the number of enrolled patients in each treatment group.

Table 14.1.2 Number of patients in the ITT, PP, and safety populations

		Treatment	
		DFP+DFP	DFO+DFP
ITT population	LIC	xxx	xxx
	Cardiac MRI T2*	xxx	xxx
	Serum Ferritin	xxx	xxx
PP population	LIC	xxx	xxx
	Cardiac MRI T2*	xxx	xxx
	Serum Ferritin	xxx	xxx
Safety population		xxx	xxx

Data source: 16.2.10 Listing of LIC, 16.2.11 Listing of cardiac MRI T2*, and 16.2.16 Listing of serum ferritin, and 16.2.24 Listing of exposure

Table 14.1.3 Number of patients by study site

Study Site	Treatment	
	DFP+DFP	DFO+DFP
001	xxx	xxx
002	xxx	xxx
...
Total	xxx	xxx

Data source: 16.2.2 Listing of demographics

Table 14.1.4 Reasons for not completing the study

	Reason	Treatment	
		DFP+DFP	DFO+DFP
N (%)		xx (100)	xx (100)
Adverse event	Detail		
	Ccccc	xx (xx)	xx (xx)
	Ccccc	xx (xx)	xx (xx)
Voluntary withdrawal	Ccccc	xx (xx)	xx (xx)
	Ccccc	xx (xx)	xx (xx)
Lost to follow-up	Ccccc	xx (xx)	xx (xx)
	Ccccc	xx (xx)	xx (xx)
Investigator decision	Ccccc	xx (xx)	xx (xx)
	Ccccc	xx (xx)	xx (xx)
Protocol violation	Ccccc	xx (xx)	xx (xx)
	Ccccc	xx (xx)	xx (xx)
Other	Ccccc	xx (xx)	xx (xx)
	Ccccc	xx (xx)	xx (xx)
Total		xx (xx)	xx (xx)

Data source: 16.2.18 Listing of disposition

Table 14.1.5 Demographics data

	Treatment		p-value [§]
	DFP+DFP	DFO+DFP	
N	Xxx	xxx	
Age (years): Mean \pm SD (Min, Median, Max)	xx.x \pm xx.x (xx.x, xx.x, xx.x)	xx.x \pm xx.x (xx.x, xx.x, xx.x)	0.xxxx
Sex: n (%) Female Male	xx (xx) xx (xx)	xx (xx) xx (xx)	0.xxxx
Ethnic Origin: n (%) Hispanic/Latino Other	xx (xx) xx (xx)	xx (xx) xx (xx)	0.xxxx

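### The Group 1 Year 1 efficacy test is run on patients partly selected on that same Year 1 outcome, and patients who did not continue are not shown

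*SAP*

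**What the plan says.** SAP 6.3.3 plans, for each of the three iron measures, a change from baseline that "will be tested against no change using a one-sample t-test". The time points are Year 1 and Year 2 for both groups and Year 3 for Group 1. SAP 6.1.2 sets the Group 1 baseline at the LA38-0411 baseline visit and takes the Group 1 Year 1 change from LA38-0411. Extension Week 0, which is also the last LA38-0411 visit, is Year 1 for this group. Group 2's baseline is extension Week 0.

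Entry to the extension requires "Completed study LA38-0411" (Protocol 4.2), and Protocol 4.5.2 adds: "The only individuals eligible for enrollment are those who completed treatment in study LA38-0411". Exclusion criterion 4 in Protocol 4.3 removes "Treatment failure after 1 year on deferiprone which in the investigator's judgment indicates the need" for a different chelator.

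On who is analysed, SAP section 3 describes Group 1 as those who carried on into the extension: "Patients who had been treated with deferiprone during LA38-0411 continued to receive deferiprone for up to 2 years (Group 1"). Protocol 9.5 says: "All patients who were enrolled and treated with the study drug, including those who withdrew early, will be eligible for inclusion". The SAP shells have only DFP+DFP and DFO+DFP columns, and the disposition shell states: "Percentages are based on the number of enrolled patients in each treatment group". SAP 6.2.1, however, reads: "The ITT population will include all randomized patients who received at least one dose of study drug", although SAP 4.1 says that treatment assignment does not apply in this study.

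**The concern.** For Group 1, the Year 1 value is known, or nearly known, when entry is decided, and one entry rule is a judgement about Year 1 response. If only continuers are analysed, patients judged to have failed are taken out, and the mean change of those left is then tested against zero. A significant Year 1 change could partly reflect who continued. The Year 1 responder rates are exposed in the same way.

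Group 2 does not carry this filter on its deferiprone response, because its baseline is set at entry. A Group 1 versus Group 2 comparison at Year 1 of deferiprone would therefore compare differently selected sets.

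The reader cannot judge the effect. SAP 6.3.1 and Table 14.1.1 begin at enrolment. No planned table or listing gives the number of LA38-0411 deferiprone patients who did not enrol, or why.

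**Working it through.** **Who is in the test.** Four places point to continuers: SAP section 3, Protocol 9.5, the DFP+DFP columns of the efficacy shells, and Table 14.1.2, which counts the ITT set in those columns only. Against them stands the single word *randomized* in SAP 6.2.1 (also in Protocol 9.3.1). A deferiprone patient who never entered the extension has no column in any shell.

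**Whether selection overlaps the outcome.** The Year 1 change ends at the visit where entry is decided. Criterion 4 concerns response over the same year. Three things make the overlap partial:
- Criterion 4 is investigator judgement.
- Protocol 3.3 foresees non-improving patients who still enrol.
- Protocol 5.1 says Visit 1 results may arrive late, so the judgement may rest on earlier values.

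**Direction.** Removing judged failures should move mean LIC and ferritin change toward benefit. For cardiac T2* the link is weaker, since Protocol 1.1.1 says cardiac iron overload is not frequent in SCD. Patients may also leave for unrelated reasons. If equal shares of best and worst responders left, the mean shift would be zero.

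**Illustrative size.** The plan gives no figure to reproduce: the extension has no power calculation, alpha or expected rollover. From the documents: 300 planned patients at 2:1 gives 300 × 2/3 = 200 on deferiprone. Everything else is assumed:
- true mean change 0
- two-sided alpha 0.05, so 2.5% in the benefit direction
- n = 150 analysed (75% of 200)
- the worst share p removed on a standard normal score that correlates r with the Year 1 change.

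Formulas, with z the upper-p normal quantile and φ the normal density:
- λ = φ(z)/(1 − p)
- shift = r·λ (in SD)
- variance after selection = 1 − r²·(zλ + λ²)
- rejection rate toward benefit from the noncentral t with n − 1 df and noncentrality √n × shift/√variance.

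For p = 10%, r = 0.5: z = 1.2816, φ(z) = 0.1755, λ = 0.1755/0.90 = 0.195. Shift = 0.5 × 0.195 = 0.0975 SD. Variance = 1 − 0.25 × (0.2499 + 0.0380) = 0.928. Noncentrality = 12.247 × 0.0975/0.963 = 1.24, which gives 23.3%.

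| Year 1, n = 150 | p = 2% | p = 5% | p = 10% |
|---|---|---|---|
| Shift in SD, r = 0.5 | 0.02 | 0.05 | 0.10 |
| Rejection toward benefit, r = 0.5 | 4.9% | 10.0% | 23.3% |
| r = 0.3 | 3.8% | 5.9% | 10.8% |
| r = 0.1 (as may hold for T2*) | 2.9% | 3.4% | 4.3% |

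A separate simulation of 200 patients with r = 0.5 gave shifts of 0.053 and 0.097 SD with 5% and 10% removed.

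**Year 3.** The effect is diluted by the Year 1–Year 3 correlation, also assumed. With r = 0.5 and that correlation 0.5, the rates are 3.5/5.2/8.7% at n = 150 and 3.3/4.6/7.0% at n = 100, which allows for attrition.

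**Responder rate.** As an extreme case, if 10% do not continue and all of them are non-responders, a 30% rate in all treated patients becomes 0.30/0.90 = 33.3% in continuers.

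**The case against.** The strongest reply has four parts.

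1. Every extension is conditional on rollover, and the protocol says so openly. One fixed cohort over Years 1 to 3 is a legitimate display. This stands, and the fix keeps that cohort. It does not answer the Year 1 point, because LA38-0411 already holds Year 1 values that the extension did not have to filter.

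2. The primary objective is safety. Efficacy is secondary and uncontrolled, no success criterion is set, and LA38-0411 is itself the randomised confirmatory trial. This stands and limits the weight.

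3. Although SAP 6.3.3 specifies the one-sample test, the shells print a one-sample p-value only for DFO+DFP (Tables 14.2.1.3, 14.2.2.3 and 14.2.3.3). The Group 1 p-value at issue has no place in them. This is correct, and the shells need it added.

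4. Zero change is not the same as no drug effect. Protocol 7.1.1 and 7.1.3 say LIC and ferritin rise in transfusion-dependent patients without effective chelation. This is also fair: the rates above describe false rejection of zero change, not of drug inactivity.

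A reader might infer from *randomized* in SAP 6.2.1 that the choice between the whole deferiprone arm and continuers is genuinely open. The documents do not support that. One word, in a definition that does not fit a study assigning nobody, stands against consistent wording elsewhere. It is a wording error to correct.

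**Conclusion.** The point holds, as a cheap improvement of modest weight. On the natural reading, the Group 1 Year 1 test and responder rates use patients partly selected on the result being tested. The lean is likely toward benefit for LIC and ferritin and uncertain for cardiac T2*. Non-continuers are invisible in the planned tables.

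Two stronger conclusions are tempting and not supported. The first is that the Year 1 error rate is inflated to some known level. The exclusion share, correlation, analysed n and alpha are all assumed, and the illustrated Year 1 range runs from near nominal (2.9%) to 23.3%. The second is that analysing the whole deferiprone arm would remove the problem. Patients who left LA38-0411 early may have no Year 1 value, so selection by completion can remain. What goes is the selection from criterion 4 and from declining to enrol.

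Years 2 and 3 are unavoidably conditional on continuing. In the pooled last-visit test, the condition applies to the Group 1 part only.

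**What to change.** 1. In SAP 6.2.1, replace *randomized* with *enrolled in LA38-EXT*, and keep this set as the fixed cohort for Group 1 Years 1 to 3.
2. In SAP 6.2 and 6.3.3, add a separately named Year 1 set: all LA38-0411 patients randomised to and treated with deferiprone who have a baseline and a Year 1 value. Report the Year 1 change, one-sample test and responder rate in this set beside the continuers-only result. Base any Year 1 efficacy statement on it. State how many treated patients lack a Year 1 value, and say that selection by non-completion remains.
3. Add the Group 1 one-sample p-value to the efficacy shells.
4. Add to Table 14.1.1 the number of LA38-0411 deferiprone patients who did not enrol, by recorded reason including criterion 4, as far as available.
5. Footnote the Group 1 Year 2 and Year 3 rows, and the Group 1 part of the pooled last-visit test, as conditional on completing LA38-0411 and continuing.

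The cost is SAP wording, a few rows, columns and footnotes, and some added analysis of LA38-0411 data. Recorded reasons may be incomplete, and the Year 1 estimate may look less favourable. No entry rule changes and no new patient assessment is needed.

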1 INTRODUCTION

1.1 Background

Pursuant to the Accelerated Approval of Ferriprox by the FDA in October 2011, ApoPharma Inc. committed to conduct a confirmatory trial of Ferriprox (deferiprone) in transfused patients, focusing primarily on those with sickle cell disease (SCD). Study LA38-0411, currently in progress, is a 52-week, prospective, multi-center, 2-arm, randomized, parallel, open-label trial comparing deferiprone therapy to deferoxamine therapy. Once patients in that trial have completed the last study visit (Week 52), they will be invited to enroll in LA38-EXT, a 2-year extension study in which all participants will receive deferiprone.

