5 MEASUREMENTS AND EVALUATIONS

5.1 Efficacy Measurements

5.1.1 Liver Iron Concentration

MRI scans for liver iron were performed at Visit 1, Visit 5, and Visit 9 (or early termination).

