6.1.2 Secondary Endpoints

The time points for the efficacy assessments are defined below. Since the baseline measures are by definition those taken prior to the start of deferiprone therapy, “baseline” is defined differently for the two groups, as follows:

- **Group 1:** For patients who received deferiprone in LA38-0411, the baseline visit of that study will be treated as the baseline visit of LA38-EXT as well. Thus, Week 0 of the extension study will be Year 1 (i.e., the completion of one year of deferiprone treatment), Week 52 will be Year 2, and Week 104 will be Year 3 of deferiprone treatment.
- **Group 2:** For patients who received deferoxamine in LA38-0411, the start of the extension study (Week 0) will be treated as the baseline visit. For this group, therefore, Week 52 will be Year 1, and Week 104 will be Year 2 of deferiprone treatment.

Efficacy endpoints for deferiprone therapy are provided below. For Group 1, the change from baseline to Year 1 is derived from study LA38-0411. For Group 2, there is no Year 3 of deferiprone treatment.

- The change from baseline to Year 1 (both groups; Group 1 data are from LA38-0411), from baseline to Year 2 (both groups), and from baseline to Year 3 (Group 1 only) in liver iron concentration (LIC), as measured by magnetic resonance imaging (MRI)
- The change from baseline to Year 1 (both groups; Group 1 data are from LA38-0411), from baseline to Year 2 (both groups), and from baseline to Year 3 (Group 1 only) in cardiac MRI T2*
- The change from baseline to Year 1 (both groups; Group 1 data are from LA38-0411 data), from baseline to Year 2 (both groups), and from baseline to Year 3 (Group 1 only) in serum ferritin
- Responder analysis, defined as the percentage of patients who show a $\geq 20\%$ decline from baseline in LIC or serum ferritin or a $\geq 20\%$ increase from baseline in cardiac MRI T2* at Year 1 (both groups; Group 1 data are from LA38-0411), at Year 2 (both groups), and at Year 3 (Group 1 only)

In addition to the above analyses, the change from baseline to end of LA38-041 for deferoxamine and the change from baseline to end of LA38-EXT for deferiprone in Group 2 will be compared. The purpose of this analysis is to assess if deferiprone could maintain or even further improve LIC and MRI T2* after the patients were switched therapy.

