	Visit	N Mean \pm SD (Min, Max)	N Mean \pm SD (Min, Max)	P-value (T-test)
LIC (mg/g dw)	Baseline	XXX xx.x \pm xx.x (xx.x, xx.x)	XXX xx.x \pm xx.x (xx.x, xx.x)	0xxxx
	Month 6	XXX xx.x \pm xx.x (xx.x, xx.x)	XXX xx.x \pm xx.x (xx.x, xx.x)	0xxxx
	Year 1	XXX xx.x \pm xx.x (xx.x, xx.x)	XXX xx.x \pm xx.x (xx.x, xx.x)	0xxxx
	Year 2	XXX xx.x \pm xx.x (xx.x, xx.x)	XXX xx.x \pm xx.x (xx.x, xx.x)	0xxxx
	Year 3	XXX xx.x \pm xx.x (xx.x, xx.x)	XXX xx.x \pm xx.x (xx.x, xx.x)	0xxxx

Data source: 16.2.10 Listing of LIC

Table 14.2.1.2 Change in LIC at each follow-up assessment

		Treatment		
		DFP+DFP	DFO+DFP	
	Visit	N Mean \pm SD (Min, Max)	N Mean \pm SD (Min, Max)	P-value (T-test)
Change in LIC (mg/g dw)	Month 6	xxx xx.x \pm xx.x (xx.x, xx.x)	xxx xx.x \pm xx.x (xx.x, xx.x)	0xxxx
	Year 1	xxx xx.x \pm xx.x (xx.x, xx.x)	xxx xx.x \pm xx.x (xx.x, xx.x)	0xxxx
	Year 2	xxx xx.x \pm xx.x (xx.x, xx.x)	xxx xx.x \pm xx.x (xx.x, xx.x)	0xxxx
	Year 3	xxx xx.x \pm xx.x (xx.x, xx.x)	xxx xx.x \pm xx.x (xx.x, xx.x)	0xxxx

Data source: 16.2.10 Listing of LIC

Table 14.2.1.3 Change in LIC for DFO+DFP group – Data from the extension study

		DFO+DFP	
	Visit	N Mean \pm SD (Min, Max)	P-value (One sample T-test)
Change in LIC (mg/g dw)	From Year 1 to Year 2	xxx xx.x \pm xx.x (xx.x, xx.x)	0xxxx
	From Year 1 to Year 3	xxx xx.x \pm xx.x (xx.x, xx.x)	0xxxx

Data source: 16.2.10 Listing of LIC

Table 14.2.1.4 Change in LIC for DFO and DFO+DFP groups

		Treatment		
		DFO*	DFO+DFP*	
	Visit	N Mean \pm SD (Min, Max)	N Mean \pm SD (Min, Max)	P-value (T-test)
Change in LIC (mg/g dw)	End of Study	xxx xx.x \pm xx.x (xx.x, xx.x)	Xxx xx.x \pm xx.x (xx.x, xx.x)	0xxxx

Data source: 16.2.10 Listing of LIC

Note: *Patients in DFO come from LA38-0411 and patients in DFO+DFP comes from LA38-EXT.

Table 14.2.1.5 Responder analysis in LIC defined as $\geq 20\%$ decline in LIC from baseline.

		Treatment				
		DFP+DFP		DFO+DFP	P-value (Fisher's exact test)	
		N	n (%)	N	n (%)	0xxxx
Year 1	xxx	xx (xx%)	xxx	xx (xx%)	0xxxx	0xxxx
Year 2	xxx	xx (xx%)	xxx	xx (xx%)	0xxxx	0xxxx
Year 3	xxx	xx (xx%)	xxx	xx (xx%)	0xxxx	0xxxx

Data source: 16.2.10 Listing of LIC

Table 14.2.1.6 Responder analysis in LIC defined as $\geq 20\%$ decline in LIC from baseline for DFO+DFP group – Data from the extension study.

		Treatment	
		DFO+DFP	
		N	n (%)
Year 1	xxx	xx (xx%)	
Year 2	xxx	xx (xx%)	

Data source: 16.2.10 Listing of LIC

Table 14.2.2.1 Cardiac MRI T2* at each assessment

		Treatment		
		DFP+DFP	DFO+DFP	

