	Visit	N Mean \pm SD (Min, Max)	N Mean \pm SD (Min, Max)	P-value (T-test)
Cardiac MRI T2* (ms)	Baseline	XXX XX.X \pm XX.X (xx.x, xx.x)	XXX XX.X \pm XX.X (xx.x, xx.x)	0xxxx
	Month 6	XXX XX.X \pm XX.X (xx.x, xx.x)	XXX XX.X \pm XX.X (xx.x, xx.x)	0xxxx
	Year 1	XXX XX.X \pm XX.X (xx.x, xx.x)	XXX XX.X \pm XX.X (xx.x, xx.x)	0xxxx
	Year 2	XXX XX.X \pm XX.X (xx.x, xx.x)	XXX XX.X \pm XX.X (xx.x, xx.x)	0xxxx
	Year 3	XXX XX.X \pm XX.X (xx.x, xx.x)	XXX XX.X \pm XX.X (xx.x, xx.x)	0xxxx

Data source: 16.2.11 Listing of cardiac MRI T2*

Table 14.2.2.2 Change in cardiac MRI T2* at each follow-up assessment

		Treatment		
		DFP+DFP	DFO+DFP	
	Visit	N Mean \pm SD (Min, Max)	N Mean \pm SD (Min, Max)	P-value (T-test)
Change in cardiac MRI T2* (ms)	Month 6	XXX xx.x \pm xx.x (xx.x, xx.x)	XXX xx.x \pm xx.x (xx.x, xx.x)	0xxxx
	Year 1	XXX xx.x \pm xx.x (xx.x, xx.x)	XXX xx.x \pm xx.x (xx.x, xx.x)	0xxxx
	Year 2	XXX xx.x \pm xx.x (xx.x, xx.x)	XXX xx.x \pm xx.x (xx.x, xx.x)	0xxxx
	Year 3	XXX xx.x \pm xx.x (xx.x, xx.x)	XXX xx.x \pm xx.x (xx.x, xx.x)	0xxxx

Data source: 16.2.11 Listing of cardiac MRI T2*

Table 14.2.2.3 Change in cardiac MRI T2* for DFO+DFP group – Data from the extension study

		DFO+DFP	
	Visit	N Mean \pm SD (Min, Max)	P-value (One sample T-test)
Change in cardiac MRI T2* (ms)	From Year 1 to Year 2	XXX xx.x \pm xx.x (xx.x, xx.x)	0xxxx
	From Year 1 to Year 3	XXX xx.x \pm xx.x (xx.x, xx.x)	0xxxx

Data source: 16.2.11 Listing of cardiac MRI T2*

Table 14.2.2.4 Change in cardiac MRI T2* for DFO and DFO+DFP groups

		Treatment		
		DFO*	DFO+DFP*	
	Visit	N Mean ± SD (Min, Max)	N Mean ± SD (Min, Max)	P-value (T-test)
Change in cardiac MRI T2* (ms)	End of Study	xxx xx.x ± xx.x (xx.x, xx.x)	Xxx xx.x ± xx.x (xx.x, xx.x)	0.xxxx

Data source: 16.2.11 Listing of cardiac MRI T2*

Note: *Patients in DFO come from LA38-0411 and patients in DFO+DFP comes from LA38-EXT.

Table 14.2.2.5 Responder analysis in cardiac MRI T2* defined as $\geq 20\%$ increase in cardiac MRI T2* from baseline.

	Treatment				P-value (Fisher's exact test)
	DFP+DFP		DFO+DFP		
	N	n (%)	N	n (%)	0.xxxx
Year 1	xxx	xx (xx%)	xxx	xx (xx%)	0.xxxx
Year 2	xxx	xx (xx%)	xxx	xx (xx%)	0.xxxx
Year 3	xxx	xx (xx%)	xxx	xx (xx%)	0.xxxx

Data source: 16.2.11 Listing of cardiac MRI T2*

Table 14.2.2.6 Responder analysis in cardiac MRI T2* defined as $\geq 20\%$ increase in cardiac MRI T2* from baseline for DFO+DFP group – Data from the extension study.

	Treatment	
	DFO+DFP	
	N	n (%)
Year 1	xxx	xx (xx%)
Year 2	xxx	xx (xx%)

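### The Group 2 deferoxamine-versus-deferiprone comparison sets a 52-week change against a change of up to 104 weeks, so equal yearly effects can give a significant difference

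*SAP*

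**What the plan says.** SAP 6.1.2 and 6.3.3 add a comparison within Group 2, the patients who took deferoxamine in LA38-0411 and switched to deferiprone in the extension. The deferoxamine change from baseline to the end of the parent study and "the change from baseline to end of LA38-EXT for deferiprone in Group 2 will be compared". SAP 6.1.2 gives the purpose: "to assess if deferiprone could maintain or even further improve LIC and MRI T2* after the patients were switched therapy".

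The two periods are fixed elsewhere:
- Protocol 1.1: LA38-0411 "is a 52-week, prospective, multi-center, 2-arm, randomized, parallel, open-label trial comparing deferiprone therapy to deferoxamine therapy".
- SAP 6.1.2: the Group 2 deferiprone baseline is extension Week 0, Week 52 is Year 1 and Week 104 is Year 2.
- SAP 5.1.1 and 5.1.2: extension MRI is done at Visits 1, 5 and 9 (Weeks 0, 52 and 104) or at early termination.

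Shells 14.2.1.4 (LIC) and 14.2.2.4 (cardiac T2*) have one end-of-study row, a separate N for each column and a p-value labelled only as a t-test. Their footnote reads "Patients in DFO come from LA38-0411 and patients in DFO+DFP comes from LA38-EXT". The shells for the post-switch change alone, 14.2.1.3 and 14.2.2.3, label their test as one-sample.

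**The concern.** The two changes accumulate over different lengths of time, and neither the text nor the shells annualise, match or adjust for this. A patient whose iron load improves steadily and is unaffected by the switch shows about twice the improvement on deferiprone, simply because that period is twice as long. If iron load worsens steadily, the same arithmetic counts against deferiprone. If deferiprone's yearly effect were half that of deferoxamine, the expected difference would be zero and the comparison would miss it.

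The test is also unnamed. The separate Ns and the unqualified label suggest a two-sample t-test, but SAP 17 says the shells may change, so this is not proven. Continuing Group 2 patients appear in both columns and share one scan, because the last LA38-0411 visit is extension Visit 1. A two-sample test would ignore that.

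This is the only formal contrast of the two drugs within Group 2. Tables 14.2.1.3 and 14.2.2.3 test the post-switch change only against zero.

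**Working it through.** The plan states no power, effect size, SD or alpha for this comparison, so there is no figure of its own to reproduce. The question is how often p<0.05 arises when the yearly effect of the two drugs is the same.

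**Inputs from the documents**
- Deferoxamine period: 52 weeks = 1 year (Protocol 1.1).
- Deferiprone period: up to 104 weeks = 2 years (SAP 6.1.2).
- Deferoxamine patients: 300 randomised 2:1 (Protocol 1.2), so at most 300/3 = 100.

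**Assumptions**
- Two-sided alpha of 0.05.
- n = 50, 75 or 100 per column.
- A common, constant yearly change s of 0.1 or 0.3, in units of the SD of the one-year change.
- Ratio r of the SD of the deferiprone change to the SD of the one-year change: 1 or 1.41 (√2), and 2 as a wide case.
- Mean deferiprone duration d of 2.0 years, or 1.8 years if 20% stop at Week 52 (0.8 × 2 + 0.2 × 1 = 1.8).

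**Expected changes.** Deferoxamine: s. Deferiprone: s × d. Their ratio is 2.0 for completers and 1.8 with the assumed dropout. The spurious difference is s(d − 1).

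**Chance of p<0.05, two-sample t-test, zero correlation.** Noncentral t with 2n − 2 degrees of freedom and noncentrality s(d − 1)/√((1 + r²)/n). Example: s = 0.3, d = 2, r = 1, n = 75 gives 0.3/√(2/75) = 0.3/0.163 = 1.84, and a rejection probability of 0.446.

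| Duration d, SD ratio r | s = 0.1; n = 50/75/100 | s = 0.3; n = 50/75/100 |
|---|---|---|
| 2.0, 1 | 8/9/11% | 32/45/56% |
| 1.8, 1 | 7/8/9% | 22/31/39% |
| 2.0, 1.41 | 7/8/9% | 23/32/41% |
| 1.8, 1.41 | 6/7/8% | 16/22/28% |
| 2.0, 2 | 6/7/7% | 16/21/27% |

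With a mean deferiprone period of only 78 weeks (d = 1.5, r = √1.5) and s = 0.3, the chance is 12.4% at n = 70.

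**Correlated columns** (same patients in both, d = 2, r = 1, simulated with 20,000 trials per cell):
- Correlation −0.5: 14/15/17% at s = 0.1 and 35/46/55% at s = 0.3.
- Correlation +0.5: 2/3/4% at s = 0.1 and 25/42/59% at s = 0.3.

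**Effect of ignoring the pairing alone.** With equal mean changes, the large-sample size of a nominal 5% two-sample test is 2(1 − Φ(1.96/√(1 − ρ))). This is 11% at ρ = −0.5, 5% at 0 and 0.6% at +0.5. If 25 of 100 deferoxamine patients do not continue, simulation gives 10.3%, 5.0% and 0.9%. A paired test stays between 4.7% and 5.3%.

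**Pairing without matching the periods.** At s = 0.3, d = 2, r = 1 and n = 100, a paired test rejects in about 40%, 56% and 84% of trials at correlations −0.5, 0 and +0.5. Pairing does not remove the duration bias.

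**Equal periods.** Comparing the two 52-week changes, or dividing the two-year change by 2, gives simulated rejection of 4.8% to 5.2% for s from 0 to 0.5 (n = 70, uncorrelated periods).

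**The case against.** The mismatch itself is hard to dispute. The case against concerns its size and weight.

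- **The rates rest on assumptions.** This stands. The documents supply only the ceiling of about 100 patients. The bias needs a non-zero yearly change that continues into the second year. Protocol 1.1.1 says cardiac iron overload is not frequent in SCD, so the mean T2* change, and with it the inflation for T2*, may be small. At correlation +0.5 and 0.1 SD per year the two-sample rate falls below 5%. Combining less favourable assumptions lowers the rates, but 16/22/28% at 0.3 SD is still well above nominal.
- **The two-sample reading is not proven, and overlap may be complete.** This also stands. SAP 6.3.3 limits the comparison to Group 2, which SAP 3 describes as patients who switched, so the footnote may only name data sources. The pairing figures are conditional and secondary; the duration problem does not depend on them.
- **Equal periods can be read side by side.** Tables 14.2.1.3 and 14.2.2.3 show the first deferiprone year (labelled Year 1 to Year 2), and the deferoxamine column shows its 52 weeks. That helps a careful reader, but the only p-value between the drugs still comes from unequal periods.
- **Decision weight is limited.** This is an added efficacy comparison in an open-label safety extension, and the randomised comparison belongs to LA38-0411. That limits the severity but does not justify a biased test.

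**Conclusion.** The concern holds. As written, the comparison cannot separate drug from duration, and the test is not specified. With the same steady yearly change on both drugs, the expected deferiprone change is 2.0 times the deferoxamine change for completers, or 1.8 times if 20% stop at Week 52. Across the zero-correlation table above, the chance of a spurious p<0.05 is 6% to 11% at 0.1 SD per year and 16% to 56% at 0.3 SD per year. All these rates depend on assumed effects, SDs, correlations and numbers. Duration causes no inflation if the yearly change is zero or if all change stops after the first year.

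This should be fixed before analysis. It does not touch the primary safety objective, but it does affect any claim that deferiprone maintained or improved on what deferoxamine achieved.

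**What to change.** In SAP 6.1.2, 6.3.3 and Tables 14.2.1.4 and 14.2.2.4:

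- Compare equal periods in the same patients: LA38-0411 baseline to Week 52 on deferoxamine against extension Week 0 to Week 52 on deferiprone.
- Name the test: a paired t-test on the within-patient difference between the two changes, with its 95% CI.
- Restrict it to Group 2 patients with all three MRI values: LA38-0411 baseline, the shared Week 0 scan and extension Week 52. Say that an early-termination scan before Week 52 does not count as the Week 52 value, and report how many Group 2 patients are excluded for a missing scan.
- Show the Week 104 change descriptively or annualised.

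The cost is SAP wording and two re-programmed tables; the Visit 5 liver and cardiac MRI are already scheduled. The downsides are that Week 104 leaves the formal test and that patients without all three scans drop out, which selects those who stayed through the first deferiprone year. It remains a before-after comparison, and the report should say so.
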